2.1. Overall Study Design and Plan

This is a randomized, double-blind, placebo-controlled, parallel group, multi-site study in non-hospitalized adult subjects who test positive for SARS-CoV-2 and have COVID-19 symptom onset within 5 days of randomization and who are not at high risk for progression to severe COVID-19. Subjects can be vaccinated or unvaccinated for COVID-19. Subjects with prior COVID-19 infection <90 days before enrollment and/or who received a COVID-19 vaccine dose <90 days before enrollment are excluded from trial participation.

[figure not shown]
Subjects will be randomized in a 1:1:1 ratio to receive either EDP 235 [REDACTED], EDP 235 [REDACTED], or placebo orally once daily for 5 days. Randomization will be stratified by age (≤ 50 years or 51 to 64 years) and by the duration of COVID-19 symptoms (≤ 3 days or >3 days and ≤ 5 days).

The study includes 4 periods:

- Screening period will occur from Day -1 to Day 1. Screening should be completed as soon as possible, and the subject will be randomized within 24 hours of signing the ICF. A subject will be considered enrolled at the time of randomization.
- Treatment period will begin with the first dose of study treatment on Day 1 and will conclude with the end-of-treatment (EOT) visit on Day 5.
- Follow-up period will begin following the last dose of study treatment and will conclude at the end of follow-up (EOFU) visit on Day 33 (28 days after the last dose of study treatment).
- Long-term follow-up period (LTFU) will begin at Day 34 and concludes at the end-of-study (EOS) visit at Week 24.

An overview of the study design is shown in **Figure 1**. Study site visits and assessments are detailed in the Schedule of Study Procedures ([Appendix 14.1](#)).

Figure 1: Study Design

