| 
Secondary Objectives
 
 To evaluate the effect of EDP 235 on COVID-19 clinical symptoms and outcomes | 
Secondary Endpoints
 
 Time to improvement of targeted COVID-19 signs/symptoms using the COVID-19 Symptom Diary through Day 33 Proportion of subjects with targeted COVID-19 signs/symptom improvement using the COVID-19 Symptom Diary through Day 33 Change from baseline in targeted COVID-19 signs/symptom score using the COVID-19 Symptom Diary through Day 33 Proportion of subjects with medically attended visits for COVID-19 through Day 33 Proportion of subjects requiring hospitalization (defined as ≥ 24 hours of acute care) for COVID-19 through Day 33 Proportion of subjects who require hospitalization and mechanical ventilation (invasive and non-invasive) through Day 33 Proportion of subjects with any of the following COVID-19 related events or all-cause mortality through Day 33 
 complications based on the investigator’s assessment medically attended visits hospitalizations intensive care unit (ICU) admissions requirement for supplemental oxygen or increased in supplemental oxygen requirement requirement for mechanical ventilation (invasive and non-invasive) |
| 
 To evaluate the effect of EDP 235 on SARS-CoV-2 viral load | 
 Change from baseline in SARS-CoV-2 RNA viral load through Day 33 Change from baseline in infectious SARS-CoV-2 viral load through Day 33 AUC of SARS-CoV-2 RNA viral load through Day 33 Proportion of subjects with SARS-CoV-2 RNA viral load target not detected (TND) over time through Day 33 Time to SARS-CoV-2 RNA TND through Day 33 |
| 
 To evaluate the pharmacokinetics of EDP 235 | 
 Plasma concentrations of EDP 235 |
| [REDACTED] | [REDACTED] |

concentration) of 5.8 ± 3.7 nM. Oral EDP 235 treatment in repeat dose, general nonclinical toxicity studies at up to 14 days of once-daily dosing across species was well-tolerated.

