3.1. Incomplete and Missing Data

Imputation rules for missing dates of prior/concomitant medications, including COVID-19 vaccinations and prohibited medications, and procedures are provided in [Appendix 14.5](#).

Imputation rules for missing AE data are provided in [Appendix 14.5](#).

Data that are continuous in nature but are reported in the form $<x$, $>x$, $\leq x$, or $\geq x$ (where x is considered as the limit of quantitation) will be set to limit of quantitation value with the following exceptions:

- Efficacy endpoint data will be imputed as detailed in [Appendix 14.5](#).
- PK concentrations data will be imputed as detailed in [Appendix 14.5](#).

- Other incomplete/missing data will not be imputed, unless specified otherwise.

All analyses will be conducted using SAS Version 9.4 or higher. Unless otherwise stated, a two-sided test will be used at a significance level (alpha) of 0.05 for all analyses. Two-sided 95% confidence intervals (CI) will be provided when appropriate.

Summary Tables and Figures will be presented by treatment group and will be labelled as follows:

- “EDP 235 [REDACTED]”
- “EDP 235 [REDACTED]”
- “Placebo”

All subject data will be presented in individual subject data listings. Dates will be shown in subject listings as they have been recorded. Unless otherwise stated, unscheduled visit results will be included in date/time chronological order, within subject listings only. All listings will be sorted by subject number, date/time and visit. The treatment group (randomized) as well as subject’s sex and age will be stated on each listing. Unless otherwise stated, data listings will be based on all subjects randomized.

When no data are available for a table or listing, an empty page with the title will be produced with suitable text (e.g., “There are no records for this table/listing.”). For analyses where convergence or the analysis cannot be performed, “NC” (not calculable) will be presented in summary tables.

For the reporting of this study both CDISC SDTM (SDTM Implementation Guide version 3.3 or later) and ADaM (ADaM Implementation Guide version 1.3 or later) standards will be applied.

[REDACTED]

[REDACTED]

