7.4. Electrocardiogram

All Electrocardiogram (ECG) results will be summarized by treatment group and visit in the Safety population and a listing will be presented of all results with abnormalities flagged.

8. Efficacy Analysis

Unless otherwise specified, efficacy analyses will be performed using ITT-c population and the following methods will be implemented:

For time to event endpoints time and date will be used and 24 hours will be considered as a day. Descriptive statistics using the Kaplan-Meier method will include the median, 25th percentile, and 95% CIs (log-negative-log transformation). Additionally, the cumulative event rate (SE) will be summarized by treatment group and presented graphically over time. For between group comparisons, Cox Proportional Hazards models (tie handling will be addressed first using the exact method then with Efron's method if the exact method does not converge) will include treatment group, randomization stratification factors of age (≤ 50 years or 51 to 64 years) and duration of COVID-19 symptoms (≤ 3 days or >3 days and ≤ 5 days), and the baseline value of the endpoint. The hazard ratios with associated 95% CIs (Wald) and p-values (analysis of maximum likelihood estimates) comparing EDP 235 [REDACTED] versus Placebo, and EDP 235 [REDACTED] versus Placebo will be reported. Model assumptions will be checked via a log-negative-log plot and/or Schoenfeld residuals as appropriate. Subjects who do not achieve the specified endpoint will be censored with time imputed as treatment start time as follows:

COVID-19 diary:

- Subjects who have not been followed through the Day 33 visit (discontinuation from study or incomplete follow-up at the time of analysis) or completed Day 33 diary will be censored at Day 33.

Other time to event endpoints:

- Subjects who discontinued from the study will be censored at Day 33.
- Subjects who have completed the Day 33 visit will be censored at Day 33 Visit Date.

For treatment comparisons of change from baseline endpoints, analysis of covariance (ANCOVA) models will include treatment group, randomization stratification factors of age (≤ 50 years or 51 to 64 years) and duration of COVID-19 symptoms (≤ 3 days or >3 days and ≤ 5 days) and baseline value of the endpoint as the covariate. The least-squares means, SE, and 95% CIs will be presented for individual groups and the difference between groups. The p-value for

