the difference between groups will also be presented. In addition, a two-sample t-test will be used to compare change from baseline between treatment without covariate adjustment (unadjusted mean difference). The p-value for the difference between groups will also be presented under the pooled test (equal variances assumption). Line graphs for both the adjusted and unadjusted means with corresponding 95% CIs will also be generated for secondary efficacy endpoints.

Proportional endpoints will be summarized by treatment group. A 2x2x2x2x2 Cochran-Mantel-Haenszel (CMH) test will be used to test the association treatment group (EDP 235 [REDACTED] versus Placebo) and the endpoint analyzed while taking into account randomization stratification factors of age (≤ 50 years or 51 to 64 years) and duration of COVID-19 symptoms (≤ 3 days or >3 days and ≤ 5 days). In addition to the p-value, the risk differences and associated 95% CIs will be reported (using the cmh commonriskdiff (test=mh) option in SAS PROC FREQ). A similar 2x2x2x2x2 Cochran-Mantel-Haenszel (CMH) test will be used for EDP 235 [REDACTED] versus Placebo. There is no planned multiplicity control for the analysis of efficacy endpoints.

In addition to the summaries noted above, all data will be presented in listings. If the two EDP 235 treatment groups exhibit similar efficacy, a comparison may be done between the combined EDP 235 treatment groups and placebo.

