8.2. Secondary Efficacy Endpoints

8.2.1. Proportion of Subjects with Targeted COVID-19 Signs/Symptom Improvement using the COVID-19 Symptom Diary through Day 33

The proportion of subjects demonstrating targeted COVID-19 signs/symptoms improvement through Day 33 will be summarized overall and by treatment group and CMH methods applied as described in [Section 8](#).

8.2.2. Change from Baseline in Targeted COVID-19 Signs/Symptom Total Score using the COVID-19 Symptom Diary through Day 33

Change from baseline in targeted COVID-19 signs/symptoms will be summarized for the total mean score and analyzed using the methods described in [Section 8](#).

Additionally, the 14 individual symptom scores will be summarized descriptively by study visit for each treatment group.

8.2.3. Proportion of Subjects with Medically Attended Visits for COVID-19 Through Day 33

The proportion of subjects with medically attended visits for COVID-19 through Day 33 will be summarized by treatment group and will be analyzed using the same CMH methods as described in [Section 8](#).

8.2.4. Proportion of Subjects Requiring Hospitalization (Defined as ≥ 24 Hours of Acute Care) for COVID-19 Through Day 33

The proportion of subjects requiring hospitalization for COVID-19 through Day 33 will be summarized by treatment group by treatment group and will be analyzed using the same CMH methods as described in [Section 8](#).

8.2.5. Proportion of Subjects who Require Hospitalization and Mechanical Ventilation (Invasive and Non-Invasive) Through Day 33

The proportion of subjects who require hospitalization and mechanical ventilation through Day 33 will be summarized by treatment group and will be analyzed using the same CMH methods as described in [Section 8](#).

8.2.6. Proportion of Subjects with COVID-19 Related Events or All-Cause Mortality Through Day 33

COVID-19 related events include complications based on the investigator's assessment, medically attended visits, hospitalizations, intensive care unit (ICU) admissions, requirement for supplemental oxygen or increased in supplemental oxygen requirement, requirement for mechanical ventilation (invasive and non-invasive) or all-cause mortality. The proportion of subjects with COVID-19 related events or all-cause mortality through Day 33 will be summarized by treatment group and will be analyzed using the same CMH methods as described in [Section 8](#).

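### Binary efficacy endpoints that have a baseline value are compared without adjusting for it, unlike the Cox and ANCOVA endpoints: a loss of efficiency, not of validity

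*SAP*

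**What the plan says.** SAP Section 8 sets one method for each type of efficacy endpoint.

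- Time to event: a Cox model with treatment, age stratum, symptom-duration stratum and the endpoint's baseline value.
- Change from baseline: ANCOVA with the same factors and the "baseline value of the endpoint as the covariate", plus an unadjusted t-test beside it.
- Proportions: "A 2x2x2x2x2 Cochran-Mantel-Haenszel (CMH) test will be used to test the association treatment group" and "the endpoint analyzed while taking into account randomization stratification factors of age" and symptom duration. The effect measure is also fixed: "the risk differences and associated 95% CIs will be reported (using the cmh commonriskdiff (test=mh) option in SAS PROC FREQ". No baseline value is named and no reason is given for the difference.

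Section 8.2.1 applies this to symptom improvement: the proportion "will be summarized overall and by treatment group and CMH methods applied as described in" Section 8. Table 1 also lists "Proportion of subjects with SARS-CoV-2 RNA viral load target not detected (TND) over time through Day 33". The analysis subsection for that endpoint is not in the text at hand, so only the Section 8 default can be applied to it. Section 8.3.7 sends Day 33 serostatus to the same CMH methods, although Section 5.3 derives a baseline serostatus.

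The covariates are collected. Section 3.4.3 admits a subject to ITT-c only with a quantifiable baseline viral load, and the schedule in Appendix 14.1 has a baseline symptom diary before the first dose.

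**The concern.** Two analyses of the same diary entries, and presumably of the same swabs, receive different adjustment. Time to symptom improvement is adjusted for baseline; the proportion improved is not. If baseline severity or viral load predicts the outcome, the risk difference is less precise than the data allow. A chance imbalance in baseline then enters the comparison of proportions uncorrected, while the Cox model on the same data corrects for it.

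For symptom improvement a link to baseline is plausible from the definition in Section 8.1.1.1. A symptom that is mild at baseline already meets its criterion if it stays mild, whereas a moderate or severe one has to improve.

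The table notation adds a second uncertainty: it has five two-level dimensions, but the text names four.

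**Working it through.** **Inputs from the SAP.** Section 3.1: "a two-sided test will be used at a significance level (alpha) of 0.05 for all analyses". Section 2.1: "Subjects will be randomized in a 1:1:1 ratio to receive either EDP 235" (two doses and placebo), so each dose is compared with placebo 1:1. CMH factors: age (2 levels) and symptom duration (2 levels), giving 2 × 2 = 4 strata.

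**Notation.** Treatment × endpoint × age × duration is 2x2x2x2, or 16 cells. The SAP writes 2x2x2x2x2, or 32 cells, which would need 8 strata and a fifth factor.

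**Assumed inputs.** The text at hand gives no sample size, response rate or prognostic strength, so there is no stated figure to reproduce. Assumed: 50, 75 or 100 per arm; rates 0.30 vs 0.50, 0.50 vs 0.70 and 0.10 vs 0.25, and 0.90 vs 0.97 at 75 per arm only; baseline effect of 0, 0.5, 1.0 or 1.5 log-odds per SD; no dropout; baseline independent of the two strata; outcomes generated from a logistic model.

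**Anchor.** Unadjusted power at n = 75 per arm, 0.30 vs 0.50, pooled rate 0.40:

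z = [0.20 × √75 − 1.96 × √(2 × 0.40 × 0.60)] / √(0.30 × 0.70 + 0.50 × 0.50) = (1.732 − 1.358) / 0.678 = 0.55, so power is 70.9%.

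**Simulated power (%), 75 per arm, 0.30 vs 0.50, 4,000 trials per row.**

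| Log-odds per SD | Planned CMH, 4 strata | CMH, 8 strata (baseline median split) | Logistic, Wald | Standardised risk difference |
|---|---|---|---|---|
| 0 | 70.2 | 68.5 | 70.3 | 71.2 |
| 0.5 | 70.2 | 70.6 | 72.8 | 73.6 |
| 1.0 | 69.5 | 73.1 | 76.8 | 77.5 |
| 1.5 | 70.8 | 78.4 | 83.6 | 84.3 |

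The planned CMH agrees with the anchor and gains nothing as baseline becomes more prognostic.

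**Gain of logistic adjustment over the planned CMH.** At the two mid-range rate pairs and 50 to 100 per arm: 0 to 1 point at 0 log-odds per SD, 2 to 3 at 0.5, 6 to 8 at 1.0, 10 to 15 at 1.5. At 0.10 vs 0.25: −1 to +10 points. Adding only a median split of baseline to the CMH gives −2 to +8 points at the mid-range rates.

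**What the scale means.** An odds ratio of 0.50 per log10 copies with an SD of 1.5 is 0.693 × 1.5 = 1.04 log-odds per SD. An odds ratio of 0.67 with the same SD is 0.40 × 1.5 = 0.60.

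**Near the ceiling** (0.90 vs 0.97, 75 per arm): CMH about 40%, logistic Wald 24 to 32%, standardised risk difference 43 to 51%.

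**Type I error** (75 per arm, 0.30 in both arms, 10,000 trials): CMH 4.8 to 5.0%, logistic Wald 4.9 to 5.1%, standardised risk difference 5.5 to 5.6%. The Monte Carlo standard error is √(0.05 × 0.95 / 10,000) = 0.22 points, so the excess for the risk difference is more than two standard errors. Its power figures are flattered slightly for that reason, and the logistic gains are the safer guide.

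**Chance imbalance.** One standard error of the baseline difference at 75 per arm is √(2/75) = 0.163 SD. If baseline explains 7% to 27% of outcome variance at an event rate near 0.5 (about 0.6 to 1.4 log-odds per SD), the slope is √(0.07 × 0.25) = 0.13 to √(0.27 × 0.25) = 0.26 per SD. The risk difference then moves by 0.163 × 0.13 = 2 points to 0.163 × 0.26 = 4 points. This averages to zero over trials; it is variance, not bias.

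**The case against.** A CMH test stratified on the randomization factors is a standard choice, holds its level and needs no outcome model. Section 8 never promises the same covariates for every endpoint type. Most proportions sent to the CMH (medically attended visits, hospitalization, ventilation, adverse events) have no baseline value, so one uniform rule is defensible. The endpoints that Section 8.1 calls primary for efficacy are already adjusted for baseline through Cox, and the proportions are secondary endpoints with no multiplicity control. A hazard ratio and a risk difference can differ for reasons unrelated to adjustment. All of this stands.

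The prognostic strength of the total symptom score is also not evident. Under Section 8.1.1.1 a symptom absent at baseline must stay absent, which is stricter than the rule for a mild one, so a low score does not make improvement uniformly easier. Improvement at any time through Day 33 may also lie near the ceiling, where a logistic Wald test does worse than the CMH. If viral load is correlated with symptom duration, the existing strata already capture part of the gain.

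Two stronger readings are tempting, and the SAP does not support them. A reader might infer that power is thrown away for no return. The loss is close to zero if baseline is weakly prognostic, and some forms of adjustment cost power. A reader might also infer that RNA TND is certainly tested on age and duration alone. That rests on a default across text that is not at hand, and the five-dimension notation leaves room for an unnamed factor.

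These points limit the claim but do not remove it. The SAP's own effect measure, a risk difference, can be adjusted for baseline, so the estimand does not force the omission. At mid-range rates, doing so cost almost nothing when baseline was not prognostic.

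**Conclusion.** The point holds as a matter of efficiency. For binary efficacy endpoints with a baseline value, Section 8 omits a covariate that it uses in its other two models, and gives no reason. This is documented for symptom improvement and presumed for the RNA TND proportion. The planned test remains valid.

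The size cannot be fixed from the SAP. It runs from about nothing to 10 to 15 points of power as the baseline effect goes from 0 to 1.5 log-odds per SD, given mid-range rates, 50 to 100 per arm, no dropout and baseline independent of the strata. At low or very high rates the result depends on which adjusted test is used. Type I error was checked only at a rate of 0.30 and 75 per arm. The change is worth making because it is cheap, not because the planned analysis is wrong.

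**What to change.** Before unblinding, amend Section 8 for binary efficacy endpoints that have a baseline value:

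- Fit a logistic model with treatment, age stratum, symptom-duration stratum and the baseline value (total symptom score for improvement, log10 viral load for RNA TND). Report the standardised (marginal) risk difference with its 95% CI.
- Base the test on that risk difference, not on the logistic Wald coefficient. Use a small-sample-corrected or bootstrap standard error, given the type I error of about 5.5%.
- Keep the CMH as supportive. Make it the sole analysis under a stated numeric rule, for example fewer than a set number of events or non-events in either arm, or non-convergence.
- Correct 2x2x2x2x2 to match the four named dimensions, or name the fifth factor.

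Cost: a few lines of SAP text, one extra model per endpoint, and reliance on the fallback at visits with extreme rates.

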8.1. Primary Efficacy Endpoints

The primary efficacy endpoints are as follows:

- Time to improvement of targeted COVID-19 signs/symptoms using the COVID-19 Symptom Diary through Day 33
- Time to SARS-CoV-2 RNA Viral Load TND Assessed by RT-qPCR

8.1.1. Primary Analyses

8.1.1.1. Time to Improvement of Targeted COVID-19 Signs/Symptoms using the COVID-19 Symptom Diary through Day 33

Improvement of targeted COVID-19 signs/symptoms is defined by the following the event occurring on the first of 2 consecutive days or on Day 33 when the following criteria are met:

- All symptoms scored as mild, moderate or severe at baseline are scored as mild or absent
- All symptoms scored as absent at baseline are scored as absent

Time to improvement of targeted COVID-19 signs/symptoms through Day 33 will be summarized graphically using Kaplan-Meier plots and analyzed by the Cox proportional hazard model as described in [Section 8](#).

8.1.1.2. Time to SARS-CoV-2 RNA Viral Load TND Assessed by RT-qPCR through Day 33

Time to SARS-CoV-2 RNA to TND is defined as the time between the date of the first dose to the first date of achieving viral load TND.

Time to SARS-CoV-2 RNA TND will be analyzed as described in [Section 8](#).

8.1.2. Sensitivity Analyses

The primary analyses above will be conducted on the PP population as a sensitivity analyses.

8.1.3. Subgroup Analyses

Subgroup analyses for the primary efficacy endpoints may be considered for the following baseline variables, if there are enough subjects in the subgroups to support the planned analyses:

- Sex (female vs male)
- Age (≤ 50 years of age vs 51 to 64 years of age)
- SARS-CoV-2 Vaccination Status (not vaccinated vs vaccinated)
- Duration of COVID-19 symptoms (≤ 3 days or > 3 days and ≤ 5 days)

The analysis for the selected primary efficacy endpoints will be analyzed as described in [Section 8](#) with the addition of a subgroup-by-treatment interaction included in the model and only the p-value of the interaction term will be reported.

8.2. Secondary Efficacy Endpoints

8.2.1. Proportion of Subjects with Targeted COVID-19 Signs/Symptom Improvement using the COVID-19 Symptom Diary through Day 33

The proportion of subjects demonstrating targeted COVID-19 signs/symptoms improvement through Day 33 will be summarized overall and by treatment group and CMH methods applied as described in [Section 8](#).

8.2.2. Change from Baseline in Targeted COVID-19 Signs/Symptom Total Score using the COVID-19 Symptom Diary through Day 33

Change from baseline in targeted COVID-19 signs/symptoms will be summarized for the total mean score and analyzed using the methods described in [Section 8](#).

Additionally, the 14 individual symptom scores will be summarized descriptively by study visit for each treatment group.

8.2.3. Proportion of Subjects with Medically Attended Visits for COVID-19 Through Day 33

The proportion of subjects with medically attended visits for COVID-19 through Day 33 will be summarized by treatment group and will be analyzed using the same CMH methods as described in [Section 8](#).

8.2.4. Proportion of Subjects Requiring Hospitalization (Defined as ≥ 24 Hours of Acute Care) for COVID-19 Through Day 33

The proportion of subjects requiring hospitalization for COVID-19 through Day 33 will be summarized by treatment group by treatment group and will be analyzed using the same CMH methods as described in [Section 8](#).

8.2.5. Proportion of Subjects who Require Hospitalization and Mechanical Ventilation (Invasive and Non-Invasive) Through Day 33

The proportion of subjects who require hospitalization and mechanical ventilation through Day 33 will be summarized by treatment group and will be analyzed using the same CMH methods as described in [Section 8](#).

8.2.6. Proportion of Subjects with COVID-19 Related Events or All-Cause Mortality Through Day 33

COVID-19 related events include complications based on the investigator's assessment, medically attended visits, hospitalizations, intensive care unit (ICU) admissions, requirement for supplemental oxygen or increased in supplemental oxygen requirement, requirement for mechanical ventilation (invasive and non-invasive) or all-cause mortality. The proportion of subjects with COVID-19 related events or all-cause mortality through Day 33 will be summarized by treatment group and will be analyzed using the same CMH methods as described in [Section 8](#).

8.2.7. Change from Baseline in SARS-CoV-2 RNA Viral Load Assessed by RT-qPCR Through Day 33

The antiviral activity of EDP 235 on viral kinetics will be measured using SARS-CoV-2 RNA viral load assessed by RT-qPCR of NP swab samples on Days 1, 3, 5, 9, 14, and 33. Change from baseline values for SARS-CoV-2 RNA viral load will be summarized using the methods described in [Section 8](#).

8.2.8. Change from Baseline in Infectious SARS-CoV-2 Viral Load Assessed by Cell Culture Infectivity Assay Through Day 33

The infectious SARS-CoV-2 viral load will be measured using a SARS-CoV-2 cell culture infectivity assay of NP swab samples on Days 1, 3, 5, 9, 14 and 33. Change from baseline values for infectious SARS-CoV-2 viral load will be summarized using the methods described in [Section 8](#).

8.2.9. AUC of SARS-CoV-2 RNA Viral Load Assessed by RT-qPCR Through Day 33

The area under the curves (AUC) from Day 1 through Day 33 will be calculated for SARS-CoV-2 viral load data using actual sampling times via non-compartmental analysis using Phoenix[®] WinNonlin[®] Version 8.3.4 or higher according to the linear trapezoidal with linear interpolation

8.3.4. AUC of SARS-CoV-2 RNAemia Viral Load Through Day 33

The area under the curve (AUC) from Day 1 through Day 33 will be calculated for SARS-CoV-2 RNAemia viral load data using actual sampling times via non-compartmental analysis using Phoenix® WinNonlin® Version 8.3.4 or higher according to the linear trapezoidal with linear interpolation. AUCs will be derived for Days 1-14 and Days 1-33. Additionally, the AUC from Day 1 through Day 14 and the AUC from Day 1 through Day 33 will be standardized for 14 and 33 days by multiplying $14, 33/t_{last}$ where t_{last} is the actual time in days of the last available assessment. No AUC values will be calculated if there are less than 3 results available. The same methods used in [Section 8.2.9](#) will be applied.

8.3.5. Time to SARS-CoV-2 RNAemia TND Through Day 33

Time to SARS-CoV-2 RNAemia to TND is defined as per [Section 8.1.1.2](#) and will be summarized and analyzed as described in [Section 8](#).

8.3.6. Change from Baseline in SARS-CoV-2 Nucleocapsid Antigenemia Through Day 33

Change from baseline of SARS-CoV-2 nucleocapsid antigenemia will be summarized as described in [Section 8](#).

8.3.7. Proportion of Subjects with Positive SARS-CoV-2 Serostatus at Day 33

The proportion of subjects with positive SARS-CoV-2 serostatus will be defined the same as baseline SARS-CoV-2 serostatus ([Section 5.3](#)) and summarized for each treatment group and will be analyzed using the same CMH methods as described for the primary endpoint in [Section 8](#).

[REDACTED]

[REDACTED]

[REDACTED]

[REDACTED]

[REDACTED]

[REDACTED]

[REDACTED]

[REDACTED]

[REDACTED]

[REDACTED]

[REDACTED]

collection. Time and date of collection will be recorded on the Plasma PK Sample Collection eCRF.

For subjects included in the PK population, the concentration data for EDP 235 will be summarized by study day, collection time relative to dose and by treatment group. Only Day 1 postdose, and Day 3 and Day 5 predose concentration data will be summarized for the PK population. Concentrations <LLOQ will be treated as zero for the computation of descriptive statistics. If more than 50% of subjects have concentration values <LLOQ, descriptive statistics will not be presented except for maximum and BQL (below quantification limit) will be displayed for mean and minimum, respectively. The number of observations, arithmetic mean, standard deviation (SD), % coefficient of variation (%CV), median, minimum, maximum, geometric mean, and %CV of the geometric mean (%GCV) will be summarized.

Mean (+/-standard error) and individual PK concentration over Study Day (Days 1, 3, and 5) by treatment group will be plotted on linear and semi-log scale.

Individual concentration data will be presented in listings.

